1.0 Objectives and Specific Aims

Goal: *To evaluate the impact of increased frequency and intensity of Physical Therapy (PT) services on patient outcomes in the acute stroke population.*

Aim I: To determine whether increasing the frequency of Physical Therapy services post-acute stroke is superior to standard of care physical therapy services; measured by a change in functional outcomes, hospital length of stay, 30 day follow up.

Hypothesis I: We hypothesize that patients receiving an increased frequency of PT services will demonstrate higher degree of improvement on the Activity Measure for Post-Acute Care (AMPAC) and Postural Assessment Stroke Scale (PASS) from admission to time of discharge from the hospital and at 30-day follow up. We also expect lower overall Modified Rankin Scale (mRS) scores for the increased frequency PT group compared the usual care PT group at 30 days post stroke.

Aim II: To determine whether increasing the intensity of Physical Therapy services post-acute stroke is superior to standard of care physical therapy services; measured by a change in functional outcomes, hospital length of stay, 30 day follow up.

Hypothesis II: We hypothesize that patients receiving an increased intensity of PT services will demonstrate higher degree of improvement on the AMPAC and PASS from admission to time of discharge from the hospital and at 30-day follow up. We also expect lower overall mRS scores for the increased frequency PT group compared the usual care PT group at 30 days post stroke.

Aim III: To determine whether increasing the intensity of Physical Therapy (PT) services post-acute stroke is superior to increasing the frequency of PT services; measured by a change in functional outcomes, hospital length of stay, 30 day follow up.

Hypothesis III: We hypothesize that patients receiving an increased intensity of PT services will demonstrate higher degree of improvement on the AMPAC and PASS from admission to time of discharge from the hospital and at 30-day follow up. We also expect lower overall mRS scores for the increased intensity PT group compared the increased frequency PT group at 30 days post stroke.

Aim IV: To determine whether increasing the intensity and frequency of PT services post-acute stroke is superior to increasing only the intensity of PT services; measured by a change in functional outcomes, hospital length of stay, 30 day follow up.

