12.0 Outcomes and Analysis

Goal enrollment is 168 participants. Based on the past literature, in similar populations the standard deviation of PASS measurements is at the most 7.20.⁵ Using this, with a sample of 42 patients in each group, with 95% confidence at the end of the study we can estimate this difference within a margin of error of 2.8.

The primary outcome measure will be the change in postural assessment stroke scale scores from time of PT evaluation to hospital discharge. A factorial design will allow for a test of intensity (vs control) and duration (vs control) through pooling across treatment arms. Using the table below, margins (A+C, B+D, A+B, C+D) need to each be 104 given a mean difference of 2.8, standard deviation of 7.2, 80% power and 5% type I error. Given that this is an early phase study, we can increase the type I error to 10% which would decrease the overall sample size needed to 168 patients (42 per arm) whilst still maintaining 80% power.

	Low Intensity	High Intensity	Totals
Low Duration	A	B	A+B
High Duration	C	D	C+D
Totals	A+C	B+D	A+B+C+D

We are planning to conduct the analysis using intention to treat paradigm. In a preliminary analysis we will compute all summary statistics. Initial plots, such as spaghetti plots, will be used to guide our analyses. A general linear mixed model approach will be used to analyze all the outcomes. This model will account for the correlations between time points using either a compound symmetric or spatial structure for the covariance matrix. Post-hoc analyses using Tukey type adjustments will be performed to obtain least squares estimates of the differences between the two randomized groups. Although the study is powered based on only the primary

outcome (PASS), we will apply multiple comparisons adjustments for the rest of the outcomes, using Bonferroni corrections. We will test for the assumptions using diagnostic procedures and take appropriate actions if needed. Also, we will define an outcome to be ‘favorable’ or ‘unfavorable’ based on a threshold and apply generalized linear mixed models with logistic link and repeat the analyses. We will attempt to minimize drop-outs but in case of missing data, we will assume Missing at Random or Missing Completely at Random. If necessary, we will perform multiple imputations. For all analyses, we will use SAS, (MIXED, GLIMMIX, MI and MIANALYZE).

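### The 80% power and the pooled tests belong to the factorial margins, while Aims I–IV compare single arms; the plan does not state the no-interaction assumption that would link the two

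*Combined protocol and SAP*

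**What the plan says.** Section 12.0 (Outcomes and Analysis) sets out a two-by-two table with A = usual care, B = intense, C = frequent and D = both. The table calls the second factor duration. The arms in Section 9.0 vary frequency, and I read it that way. The planned tests are described thus: "A factorial design will allow for a test of intensity (vs control) and duration (vs control) through pooling across treatment arms".

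The sample size applies to the margins. Each must be 104 "given a mean difference of 2.8, standard deviation of 7.2, 80% power and 5% type I error". Relaxing the error rate to 10% is said to "decrease the overall sample size needed to 168 patients (42 per arm) whilst still maintaining 80% power".

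Section 1.0 puts the questions differently. Aims I and II set more frequent and more intense therapy against standard care, and their hypotheses speak of groups. Aim III is "To determine whether increasing the intensity of Physical Therapy (PT) services post-acute stroke is superior to increasing the frequency of PT services". Aim IV is "To determine whether increasing the intensity and frequency of PT services post-acute stroke is superior to increasing only the intensity of PT services", and Hypothesis IV also sets the combined group against usual care or either single-component group. Section 2.0 gives the purpose of Phase II as attributing the Phase I gain to frequency, intensity or the two together.

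The only analysis sentence that reaches individual arms is: "Post-hoc analyses using Tukey type adjustments will be performed to obtain least squares estimates of the differences between the two randomized groups". Section 12.0 names no interaction contrast, states no assumption about interaction, and gives no power for a comparison of two arms.

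**The concern.** A margin averages over the other factor. The intensity margin mixes B with D on one side and A with C on the other, so it equals the effect of intensity alone only if adding frequency does not change that effect. Whether the combination matters is one of the questions of Phase II, so the assumption cannot be passed over in silence.

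Two things are at stake. A significant margin carries the plan's label of a test against control, and could be reported as showing that one component works by itself when the gain came from the combined arm. Readers may also attach 80% power to arm comparisons that have much less. Because the arm comparisons are post hoc and unnamed, it stays open whether margins or pairs will be taken as the answer to each aim.

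**Working it through.** **Inputs.** From Section 12.0: difference 2.8, SD 7.2, 168 patients, 42 per arm, hence 84 per margin. From Section 3.0: Phase I PASS gains of 6.28 and 1.82, a difference of 4.46. Sidedness is not stated. Two-sided is assumed because it reproduces the plan's numbers (one-sided 5% would give the same N as two-sided 10%).

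**The plan's own figures.** n per margin = 2(z₁₋α/₂ + z₀.₈)²(7.2/2.8)².
- 5%: 2 × (1.960 + 0.842)² × 6.612 = 103.8, so 104, as stated.
- 10%: 2 × (1.645 + 0.842)² × 6.612 = 81.8, so 82, or 164 in total; the plan has 168.
- Power with 84 v 84: SE = 7.2√(2/84) = 1.111; 2.8/1.111 = 2.520; Φ(2.520 − 1.645) = 0.809.

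**Arm contrasts (C−A, B−A, B−C, D−B).** SE = 7.2√(2/42) = 1.571; 2.8/1.571 = 1.782.

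| Rule | Critical value | Power for 2.8 |
|---|---|---|
| Unadjusted, 10% | 1.645 | 55% |
| Unadjusted, 5% | 1.960 | 43% |
| Tukey, four arms, 10% | 2.310 | 30% |
| Tukey, four arms, 5% | 2.596 | 21% |

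The Tukey critical values are q(4, 164)/√2, with power from the noncentral t. The difference detectable with 80% power at 10% is (1.645 + 0.842) × 1.571 = 3.9 points unadjusted, and (2.310 + 0.842) × 1.571 = 4.95, about 5.0, with Tukey.

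**What a margin estimates.** Let I = D − C − B + A. Then:
- intensity margin = (B − A) + I/2
- frequency margin = (C − A) + I/2
- D − B = frequency margin + I/2

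If I = 0, the margins answer Aims I, II and IV. For Aim III, intensity margin minus frequency margin = B − C whatever I is, so its precision is always that of 42 v 42.

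**Can the margins tell the explanations apart?** Take a combined effect of 4.46 and write the means as (A, B, C, D):
- combination only: (0, 0, 0, 4.46), I = 4.46
- additive: (0, 2.23, 2.23, 4.46), I = 0
- either alone suffices: (0, 4.46, 4.46, 4.46), I = −4.46

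All three give both margins 2.23. Each margin test then has power Φ(2.23/1.111 − 1.645) = 64%, and both are significant in about 0.64² = 41% of trials, in every pattern.

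**Can the planned Tukey pairs tell them apart?** Simulated at 10%, with 200,000 trials per pattern:

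| Pattern | D>B or D>C | B>A or C>A |
|---|---|---|
| Combination only | 84% | 2% |
| Additive | 30% | 30% |
| Either suffices | 2% | 84% |

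**Interaction.** SE = 7.2√(4/42) = 2.22. Power for I = 2.8 at 10% is Φ(2.8/2.22 − 1.645) = 35%; 80% power needs about 2.487 × 2.22 = 5.5 points.

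**Arm-level precision statement.** Section 12.0 gives a 95% margin of error of 2.8 with 42 per group. For a difference between two arms it is 1.96 × 1.571 = 3.08.

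**The case against.** A reader might infer that the trial cannot show which component drives the benefit, and that the 80% power applies to none of the four aims. The documents do not support either statement.

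First, Aims I and II can be read at factor level, although their hypotheses lean towards groups. Without interaction, the margins answer Aims I, II and IV with about 81% power for 2.8 points. Second, the plan does foresee arm comparisons. A Tukey adjustment makes sense only with more than two groups, so the reference to two groups is best read as a slip for all pairs. On the extreme patterns those pairs point the right way in about 84% of trials. A report of two effective components when neither works alone would have to ignore the plan's own comparisons.

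Third, the SD of 7.2 is given as an upper bound, and for PASS measurements rather than change. At an assumed SD of 2.8/(2.487 × √(2/42)) = 5.16, 42 v 42 reaches 80% unadjusted at 10%. A raw change score whose two measurements correlate below 0.5 would have an SD above 7.2, so the uncertainty runs both ways. Fourth, the plan calls this an early phase study.

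These points limit the criticism but do not remove it. The no-interaction assumption is nowhere stated. The Tukey step is post hoc and names no contrasts. It leaves the additive pattern ambiguous, and it has 30% power for the difference on which the trial was sized.

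**Conclusion.** The concern holds in limited form and should be fixed. The stated 80% power is correct for a pooled margin (about 81%). For the arm contrasts in which the aims are worded it is 55% unadjusted, or 30% with the planned Tukey adjustment, for 2.8 points at two-sided 10%. Reading a margin as the effect of one component against control needs an unstated assumption that the trial is partly meant to examine, and Aim III has arm-level precision in any case. Large combination-only or either-suffices patterns would usually show in the Tukey pairs. Additive effects and a moderate combination effect would not be reliably separated.

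This rests on an SD of 7.2 applied to the change score, as the plan does, on 42 analysed patients per arm, and on reading the duration factor as frequency.

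**What to change.** In Section 12.0:

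1. State that 80% power at two-sided 10% applies to the pooled margins only, and that reading a margin as the effect of one component against control assumes no interaction.
2. From the four-cell model, pre-specify C−A, B−A, B−C and D−B for Aims I–IV under one named multiplicity rule, for example the Tukey adjustment already planned. Report D−C−B+A with its confidence interval beside the margins, as an estimate and not as a gatekeeping test, since its power for 2.8 points is only 35% at 10%.
3. Base any claim that intensity alone or frequency alone works on B−A or C−A, not on a margin.
4. Give the arm-level power under the chosen rule: 30% with Tukey (detectable difference about 5.0 points) or 55% unadjusted (3.9 points), noting that SD 7.2 is the plan's stated upper bound.
5. Replace the reference to two randomized groups with the four arms, and correct the 95% margin of error for 42 per group from 2.8 to about 3.1 for a two-arm difference.

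The cost is wording and a few contrast statements, with no extra patients and no change to the design. The downside is a less favourable stated power for the aims.

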5.0 Study Endpoints

Physical Performance and Functional Measures: PASS scores & AMPAC scores on evaluation, day three, discharge, and 30-day follow up. Discharge disposition recommended vs ultimate discharge disposition, hospital length of stay, and 30-day readmission. The primary outcome is a change in functional mobility measure- the Postural Assessment Scale for Stroke from PT evaluation to discharge from hospital.

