If a patient is randomized to the frequent AND intense physical therapy treatment group they will receive PT services 2x/day for 3 out of the first 5 days of hospital admission and daily for the remainder of the hospitalization. Sessions will be 20-50 minutes in duration (based on patient tolerance) and will focus on increasing the intensity of services by making difficult tasks more difficult with the addition of resistance or other challenges. This is known as “Error Augmentation training” and will be implemented to target at least 3 post stroke deficits identified on evaluation. If a patient is randomized to the standard of care group they will receive the normal amount of PT services one a day, three to five days week for 20-50minutes throughout admission. The patient will be assisted to perform transfers and mobility tasks with a PT providing facilitation to assist the patient without the component of an added challenge.

Functional measures such as PASS, AMPAC, mRS will be collected on initial PT evaluation, day three of treatment and discharge from the acute care hospital. These measures will be collected again in the outpatient neurology clinic (or virtually via Zoom or Doxy.me) at 30 day follow up appointment. Study procedures will end after 30 day follow up appointment is completed.

Participants can ask to end PT sessions early if they become uncomfortable or do not want to do them.

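### The mixed model allows only a compound symmetric or spatial covariance, with no rule for choosing, so the standard error of the primary PASS change may be too small or too large; single-occasion outcomes have no model of their own.

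*Combined protocol and SAP*

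**What the plan says.** Section 12.0 sets one approach: "A general linear mixed model approach will be used to analyze all the outcomes". The next sentence fixes the covariance: "This model will account for the correlations between time points using either a compound symmetric or spatial structure for the covariance matrix". No unstructured option, choice rule or robust standard error is named.

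The primary outcome is in the same section: "The primary outcome measure will be the change in postural assessment stroke scale scores from time of PT evaluation to hospital discharge". Section 5.0 gives the visits: "PASS scores & AMPAC scores on evaluation, day three, discharge, and 30-day follow up". Section 9.0 gives a matching schedule that includes mRS: "Functional measures such as PASS, AMPAC, mRS will be collected on initial PT evaluation, day three of treatment and discharge from the acute care hospital", with a further collection at 30 days. (The data list in section 10.0 leaves out discharge PASS; I follow sections 5.0, 9.0 and 12.0, which agree.)

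Section 5.0 also lists outcomes that occur once per patient: "Discharge disposition recommended vs ultimate discharge disposition, hospital length of stay, and 30-day readmission".

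Three other statements in section 12.0 bear on the point. Initial plots will guide the analyses. Assumptions will be checked with diagnostics, followed by unspecified action if needed. The analyses will also be repeated with a logistic generalized linear mixed model on a favorable/unfavorable split, for which neither the threshold nor the outcomes are given.

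**The concern.** Compound symmetry imposes one variance and one correlation on all six visit pairs. Spatial structures make correlation fall with distance in time. The visits here are evaluation, day three, discharge and 30 days. Discharge falls on a different day for each patient, and length of stay is itself an outcome. Three visits lie within the admission and one well after it, so a single correlation, or a single decay rate, may fit poorly.

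The primary test uses only one of the six pairs. Under a restricted structure its standard error is partly set by the other five. If that standard error is too small, false positives exceed a type I error that section 12.0 has already relaxed to 10%. If it is too large, the intervals are wider than the data warrant.

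The secondary issue is that a covariance between time points has no meaning for an outcome measured once, and a categorical disposition is not a linear-model response.

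**Working it through.** **The plan's own figure first.** Section 12.0 says the factorial margins "need to each be 104 given a mean difference of 2.8, standard deviation of 7.2, 80% power and 5% type I error". With n per margin = 2[SD(z for alpha + z for power)/difference]²:

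- 5% two-sided: 2[7.2(1.960 + 0.842)/2.8]² = 103.8, so 104. This matches.
- 10% two-sided: 2[7.2(1.645 + 0.842)/2.8]² = 81.8, so 82 per margin and 164 in all, against 168 stated. With 84 v 84, power is 80.9%.

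The sample size therefore reproduces and is not in question.

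**Standard error under compound symmetry.** Take complete data, four visits and equal variance σ² at each visit. The true variance of the evaluation-to-discharge change is 2σ²(1 − ρ_ED), where ρ_ED is the correlation for that pair. The compound symmetric fit uses 2σ²(1 − ρ_mean), where ρ_mean is the average over all six pairs. Hence

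k = model SE / true SE = √[(1 − ρ_mean)/(1 − ρ_ED)],

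and in large samples actual type I error = 2[1 − Φ(1.645k)].

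**Standard error under spatial power.** Correlation is ρ^|t_i − t_j|, with visits assumed at days 0, 3, 6 and 30. The best-fitting matrix in the Kullback-Leibler sense replaces the compound symmetric one, and k is formed in the same way.

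**Inputs.** σ = 7.2 comes from section 12.0 ("the standard deviation of PASS measurements is at the most 7.20"). All correlations and the discharge day of 6 are assumptions. Correlations are listed as evaluation–day 3, evaluation–discharge, evaluation–30 days, day 3–discharge, day 3–30 days, discharge–30 days.

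| Assumed pattern | ρ_mean | ρ_ED | CS: k, type I | Spatial: k, type I |
|---|---|---|---|---|
| (a) all 0.70 | 0.700 | 0.70 | 1.00, 10.0% | 1.24, 4.2% |
| (b) 0.90, 0.81, 0.729, 0.90, 0.81, 0.90 | 0.842 | 0.81 | 0.91, 13.3% | 0.88, 14.9% |
| (c) 0.90, 0.85, 0.60, 0.92, 0.62, 0.68 | 0.762 | 0.85 | 1.26, 3.8% | 1.01, 9.7% |
| (d) 0.92, 0.90, 0.50, 0.93, 0.50, 0.55 | 0.717 | 0.90 | 1.68, 0.6% | 1.20, 4.9% |
| (e) 0.80, 0.60, 0.50, 0.85, 0.75, 0.85 | 0.725 | 0.60 | 0.83, 17.3% | 0.80, 18.7% |
| (f) 0.75, 0.50, 0.40, 0.85, 0.75, 0.90 | 0.692 | 0.50 | 0.79, 19.6% | 0.76, 21.1% |

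Example, row (e): ρ_mean = 4.35/6 = 0.725; k = √(0.275/0.400) = 0.83; 2[1 − Φ(1.645 × 0.829)] = 17.3%.

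With pattern (b) and unequal SDs over visits (assumed 6 rising to 7.2, or 7.2 falling to 5), k is 0.89 to 0.91 under compound symmetry and 0.86 to 0.88 under spatial power.

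**Finite-sample check.** In 6,000 simulated trials of 4 × 42 patients, with ρ_ED = 0.60 and the other five pairs averaging 0.78 (overall mean (0.60 + 5 × 0.78)/6 = 0.75), compound symmetry rejected in 20.0% and unstructured in 10.7%. The formula gives 19.3%: k = √(0.25/0.40) = 0.79.

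**What the conservative side costs.** In row (d) the SD of change is 7.2√(2 × 0.10) = 3.22, so a difference of 2.8 is 2.8/(3.22√(2/84)) = 5.64 standard errors. Power with the inflated standard error is Φ(5.64 − 1.645 × 1.68) = 99.8%. In row (a) under spatial power, the SD is 5.58 and the ratio 3.25, so power falls from 94.6% to Φ(3.25 − 1.645 × 1.24) = 89%. In these patterns the oversized error costs precision but does not take power below the planned 80%. Inflation is the more serious direction.

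**Parameters.** Four visits need 4 × 5/2 = 10 covariance parameters when unstructured, against 2 for compound symmetry or spatial power: 8 more, estimated from 168 patients.

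**The case against.** The strongest reply is that the documents give no correlations, so nothing shows that the chosen structure will be wrong. This stands. Row (a) gives compound symmetry exactly the right standard error, and row (c) gives spatial power almost exactly the right one. A reader might infer that the primary test has a 20% false-positive rate; that figure belongs to particular assumed patterns, and others are conservative. A reader might also take the 7.2 used in the sample size as the SD of change, which would imply ρ_ED = 0.5 (7.2 = 7.2√[2(1 − 0.5)]) and so point to row (f). But section 12.0 describes 7.2 as an upper value for the SD of PASS measurements, and ρ_ED alone does not fix the other five pairs.

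Second, a spatial structure can use each patient's actual discharge day, which answers the uneven spacing directly. That helps only if correlation really decays with time in the assumed form; rows (e) and (f) show it doing no better than compound symmetry.

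Third, section 12.0 promises plots, diagnostics and a logistic mixed model, so it is wrong to say that a linear model is the only one planned. The logistic model could serve readmission or a dichotomised mRS. But it is a repeat analysis with no outcome list or threshold, and the diagnostics clause names no remedy, which leaves the covariance to be chosen after seeing the data.

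Fourth, a reader might infer that p-values from a linear model on binary or ordinal outcomes are unreliable. Nothing supports that. Simulated null comparisons of 84 v 84 at nominal 5% (40,000 runs, assumed distributions) rejected 4.1–5.2% for event rates of 5–20%, 4.8% for a seven-level mRS, and 4.5–4.8% for log-normal length of stay. The remaining objections are effect scale, efficiency and the categorical nature of disposition.

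**Conclusion.** The point holds as a risk. The plan confines the primary analysis to two restrictive covariance families without a choice rule or a named fallback. Under the assumed patterns the model-based standard error is 0.79 to 1.68 times its true value under compound symmetry and 0.76 to 1.24 times under spatial power. Actual type I error is about 1% to 20% and 4% to 21% respectively, at nominal 10%. It is correct if the chosen structure holds. These ranges rest on assumed correlations, a discharge day of 6 and complete data. With complete balanced data and a saturated arm-by-visit model the point estimate is unaffected; the issue is the standard error. This should be changed because the remedy is nearly free, not because an error has been shown.

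The secondary point holds in a narrow form. Length of stay, readmission and disposition each have one value per patient, the planned covariance does not apply to them, and no primary model for them is stated.

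**What to change.** In section 12.0, prespecify for PASS and AMPAC an unstructured covariance with visit (evaluation, day three, discharge, 30 days) as a category, and Kenward-Roger degrees of freedom. If the model does not converge, use a named simpler structure with empirical (sandwich) standard errors. State this order in advance, so that diagnostics do not decide the primary standard error.

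Add that length of stay, 30-day readmission and disposition use single-occasion models: for example, logistic regression for readmission and disposition (multinomial if disposition keeps more than two categories) and a log-scale model for length of stay. Other reasonable choices exist; what matters is that one is named for each. State which outcomes the existing logistic mixed model covers and at what threshold, and whether mRS is analysed as a score or as an ordinal outcome.

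The cost is SAP wording and eight more covariance parameters. No new data are needed and the sample size does not change. The repeated-measures models stay in the SAS procedures already listed; ordinary logistic regression is also standard SAS.

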9.0 Study Design

This study will be designed as a randomized control trial with a 1:1:1:1 randomization. This study will utilize a stratified block randomization design and stratifying on the 4 NIHSS categories to randomly allocate a participate to a treatment group, while maintaining a balance across treatment groups. All patients will be identified and consented as soon as possible, ideally within 24 hours of admission to the stroke service. Patient's blood pressures will be obtained prior to PT treatment to ensure safety of mobilization. If systolic blood pressure is above 220mmHG, therapy services will not be performed at that time and therapist will follow up later in the day once patient is medicated for hypertension by nursing staff.

If a patient is randomized to the frequent physical therapy treatment group, they will receive PT services 2x/day for 3 out of the first 5 days of hospital admission and daily for the remainder of their hospitalization. Sessions will be 20-50 minutes in duration, based on patient tolerance. These PT sessions will include working on getting out of bed, transferring from bed to a chair, working on balance, strengthening the side of the body affected by the stroke, learning how to walk again and/or how to use a wheelchair if unable to walk.

If a patient is randomized to the intense physical therapy treatment group, they will receive PT services daily with treatment sessions being more difficult than a standard therapy session. During each PT session, the things that are difficult for the patient will be made even more difficult (by adding resistance or other challenges) in order to increase the intensity of the session. This is known as "Error Augmentation training" and will be implemented to target at least 3 post stroke deficits identified on evaluation.

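### Holm's step-down procedure would keep the planned family-wise error limit for the secondary outcomes and recover some of the power that plain Bonferroni gives up

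*Combined protocol and SAP*

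**What the plan says.** Section 12.0 makes the change in PASS from PT evaluation to hospital discharge the primary outcome and sizes the trial on it alone ("Although the study is powered based on only the primary" outcome). For everything else, "we will apply multiple comparisons adjustments for the rest of the outcomes, using Bonferroni corrections". No step-down version is named, and no reason is given for choosing plain Bonferroni.

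The family is not listed. Section 5.0 gives PASS and AMPAC at several time points and then "Discharge disposition recommended vs ultimate discharge disposition, hospital length of stay, and 30-day readmission". The mRS appears in Sections 1.0 and 9.0. Neither the number of outcomes in the family nor its alpha is stated. Section 12.0 uses both 5% and 10% when discussing the primary outcome. The Tukey-type adjustment for group contrasts in the same section is a separate matter and is not questioned here.

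**The concern.** Single-step Bonferroni holds every outcome to alpha/k, however many of the others have already been rejected. Holm orders the p-values and relaxes the threshold after each rejection: alpha/k, then alpha/(k-1), and so on up to alpha. Both rest on the same probability inequality, so Holm needs no assumption about correlation that Bonferroni does not need. The sponsor's decision to adjust, and the level at which it adjusts, stay as they are.

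What is at stake is power on the supporting outcomes. Hypotheses I-IV name AMPAC, PASS and mRS, with PASS and AMPAC also at 30 days, and the Aims add length of stay. The hypotheses predict benefit on several of these together, and Holm helps only when more than one effect is real.

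**Working it through.** **1. The plan's own figure.** Inputs from Section 12.0: "given a mean difference of 2.8, standard deviation of 7.2, 80% power and 5% type I error", under which "margins (A+C, B+D, A+B, C+D) need to each be 104". The two-sided normal formula, n per margin = 2(z_alpha + z_power)² (SD/difference)², gives:

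- alpha 5%: 2(1.960 + 0.842)² (7.2/2.8)² = 103.8, so 104, as stated.
- alpha 10%: 2(1.645 + 0.842)² (7.2/2.8)² = 81.8, so 82 per margin and 164 in total, against the stated 168. With 84 per margin, power is 80.9%.

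The primary calculation therefore reproduces. There is no corresponding figure for the secondary outcomes.

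**2. Why Holm never does worse.** Take k = 5 and a family alpha of 10%. Bonferroni compares every p-value with 0.10/5 = 0.02. Holm compares the smallest with 0.02, then the next ones with 0.025, 0.033, 0.05 and 0.10, and stops at the first failure. Any p-value at or below 0.02 passes under both rules. The first step is identical, so the chance of rejecting at least one hypothesis is exactly the same.

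**3. Assumptions for sizing.** None of these is in the documents.

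- Family size k = 5 to 7. AMPAC, mRS, disposition, length of stay and readmission make five; 30-day PASS or further time points add to that.
- Common correlation 0.5.
- True effects of 2.5 standard errors. For scale, the primary's planned effect at 84 v 84 is 2.8/(7.2 × √(2/84)) = 2.52 standard errors.
- Family alpha 5% or 10%, two-sided z-tests.

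**4. Simulation** (400,000 replicates per row). Average power per true effect, Bonferroni to Holm, in percent:

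| k | Family alpha | One real | Two real | Four real | All real |
|---|---|---|---|---|---|
| 5 | 5% | 47.0 to 47.1 | 46.9 to 48.4 | 47.0 to 52.7 | 47.0 to 56.1 |
| 5 | 10% | 57.0 to 57.1 | 56.9 to 58.7 | 56.9 to 63.7 | 56.9 to 67.6 |
| 7 | 5% | 42.5 to 42.5 | 42.4 to 43.3 | 42.4 to 45.6 | 42.4 to 51.7 |
| 7 | 10% | 52.0 to 52.1 | 52.0 to 53.3 | 51.9 to 55.9 | 52.0 to 63.4 |

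The Bonferroni column can be checked by hand. For k = 7 at 10% the critical value is 2.450, and Φ(2.5 − 2.450) = 52.0%. Results for k = 6 lie between those for 5 and 7. With k = 7, correlation 0.3 changes the gains for four or seven real effects by less than one point. No simulated dataset had a Bonferroni rejection that Holm missed.

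**5. Actual family-wise error, both methods** (k = 7, four real effects). At a 10% limit: Holm 6.1%, Bonferroni 3.8%. At a 5% limit: Holm 3.1%, Bonferroni 2.0%. If no effect is real the two are identical.

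**6. Weaker effects.** At 1.5 standard errors (k = 7, four real, 10%), power goes from about 17% to 19%, a gain of under 2 points.

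**The case against.** The strongest reply is that nothing here is wrong. Bonferroni is valid, the plan sets no power target for any secondary outcome, and its conclusions would be safe. All of that stands. It makes this an efficiency point, but it gives no reason to keep the less powerful of two methods with the same guarantee.

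A second reply is that Bonferroni has simple simultaneous intervals that match its tests. With Holm, an unadjusted interval can exclude zero beside a non-significant adjusted p-value. This is a real, small cost. Section 12.0 does not plan Bonferroni-adjusted intervals for the secondary outcomes, so nothing planned is lost.

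Third, the extra power uses more of the permitted error, as step 5 of the working shows. The two methods share a nominal limit, not an actual error rate. Holm stays within that limit.

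A reader might also infer several stronger things that the documents do not support:

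- That the trial is too small for its secondary outcomes. No standard deviation, target difference or power is given for any of them.
- That the gain to expect is the one with all effects real. That needs every listed outcome, including readmission and disposition, to carry a sizeable effect.
- That length of stay is part of the hypotheses. It is named only in the Aims.
- That the plan explicitly commits to a single-step test. That is the ordinary meaning of the words, not a stated rule.

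**Conclusion.** The point holds as a cheap improvement. Under any dependence, Holm keeps the same nominal family-wise limit and rejects at least what Bonferroni rejects. The gain per true effect is about 0 points with one real secondary effect, 1 to 2 with two, 3 to 7 with four, and 9 to 11 if all are real. These figures rest on an assumed k of 5 to 7, correlation of 0.5 and effects of 2.5 standard errors. The qualitative ordering does not depend on those assumptions; the size does. It cannot be fixed from the documents while the family, its size and its alpha are undefined. That gap affects Bonferroni equally, since alpha/k cannot be applied reproducibly without alpha and k.

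**What to change.** In Section 12.0, replace the reference to Bonferroni corrections with a Holm step-down adjustment. List the secondary hypotheses that form the family (outcome, time point and contrast) and state the family alpha, before outcome data are examined by arm.

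For intervals, either label them as unadjusted or show Bonferroni intervals beside Holm-adjusted p-values, and say which.

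The cost is a short edit to the analysis section and a few lines of code to order the p-values. No added patients, data or assumptions are needed. Listing the family takes some thought, but the present wording requires that too.
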